Unfortunately, hospital-acquired weakness is highly prevalent among COVID-19 patients, who require paralytics for an extended period of time in order to maintain oxygenation. The prolonged use of these agents lead to long-term inhibition of the Acetylcholine receptors of Neuromuscular junctions. All COVID-19 ventilated patients at our institution have been on paralytics for at least 48 hours, and most of these patients receive concomitant Glucocorticoid therapy. Together Glucocorticoids and paralytics, lead to Myosin depletion and muscle atrophy. This combination has shown to be a risk factor for CINM. In a recent JAMA study on 5700 COVID-19 patients performed in NYC, 72% of the ventilated patients remained in the hospital, and only 3% of this population have been discharged. We believe that the major reason for this is the inability to wean from the ventilator and to rehabilitate due to Neuro-Myopathy.

A recent systematic review suggested the major pathways involved in CINM. These major pathways include muscle disuse due to prolonged immobilization, inflammation, impaired perfusion and oxygen delivery, and hyperglycemia. All these factors might be magnified among COVID-19 patients. Additional to muscle atrophy, a hyper-inflammatory systemic state and coagulation disorders induced by the COVID-19 virus, poor blood oxygen saturation, and poor perfusion to lower extremities are other important risk factors to be aware in these patients. As described above, this type of work may allow physicians to provide more personalized care and evaluate their interventions with a practical test.

Muscle weakness and fatigue impede patients; capacity to exercise, and are known to delay extubation, extend length of stay in hospital, and delay patients to achieve independent mobility. The goal of E-stim in advanced disease states is to prevent or reverse skeletal muscle wasting for persons who are not able to exercise. Conditions include advanced periods of mechanical ventilation.

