Will pregnant women and/or fetuses (as described in 45 CFR 46 Subpart B) be enrolled in the research? No

E4. Neonates

Will neonates of uncertain viability or nonviable neonates (as described in 45 CFR 46 Subpart B) be enrolled in the research? No

E5. Children

Will children be enrolled in the research? No

Section F: Design/Procedure

F1. Design

Select one category that most adequately describes your research: c) Pilot

Discuss the research design including but not limited to such issues as: probability of group assignment, potential for subject to be randomized to placebo group, use of control subjects, etc.

Phase I: 20 subjects with COVID-19 infection that are being treated in the hospital. This means that this patient population is positive to COVID-19 and have been admitted with no more than 48 hours to the hospital due to severe infection. In some cases, the patients will not able to consent at the time of enrollment. This determines a high grade of severity of illness. Therefore, a family member/legal representative will be contacted via telephone for consenting. Participants will be randomized to intervention (IG) or control group (CG). The entire cohort will receive daily EE in lower extremity (e.g. Gastronemius, tibial anterior muscle) up to 1 hour. EE therapy will be provided using portable device. The EE device will be functional for IG and non-functional for CG. The duration of the study will be 2 weeks or until patient discharge, whichever comes first. The primary outcomes include between group difference and change from the baseline in muscle endurance, muscle strength, lower extremity tissue oxygen saturation, neuropathy, and muscle atrophy. Outcomes will be assessed at baseline, time of discharge or 2 weeks, whichever comes first. Due to the condition of the patient we are looking to reduce the interaction with staff, the device will be placed with no additional requirements. Physical therapy targets other physical performances, this device is aimed to improve blood flow, tissue perfusion and muscle activation while the patient is non-responsive to physical activities.

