Aim1 (to understand mechanism of action): Examine immediate benefit of lower extremity EE to improve venous return flow, tissue oxygenation, and muscle activation (short term benefit). In this study, we will recruit a convenient sample of 20 hospital patients diagnosed with COVID-19 (short-term benefit).

Optional: Subjects will be assessed using Doppler ultrasound and near infrared imaging (Kent Imaging System) at pre-, 30min, 60min, and 30min post-treatment (after stopping of EE device). Lower extremity muscle activation will be assessed by using sEMG (electromyography).

Patients will begin the study after being admitted to the hospital no more than 48 hours.

Aim 2 (to examine effectiveness): Examine effectiveness of daily use of EE to treat CINM, and other associated major adverse events (MAE) including deep vein thrombosis (DVT), cardiovascular events, and death. Participants will receive standard of care plus adjunctive daily EE therapy using an FDA approved bio-electric stimulation technology (BEST) platform (Tennant Biomodulator® PRO, AVAZZIA, Inc) during the entire length of stay in hospital. The device will be provided by the research staff.

We will assess incidence of neuropathy and myopathy during hospital discharge or 2 weeks, whichever comes first. Neuropathy severity will be quantified using vibratory perception threshold (VPT) test. Myopathy will be assessed by measuring changes in calf muscle circumstance, weight change from pre-hospital admission, and sEMG. In addition, we will determine weakness using foot dynamometer and a validated frailty meter. Length of hospital stay and MAE (documented via electronic health record) will be tracked for planning of future studies. Both extremities will have all measurements and 1 hour electrical stimulation therapy at baseline. Daily treatment will performed up to 3 times per day, but no more than 1 hour in total.

Daily electrical stimulation will be administered by a nurse/staff involved in the hospital care. A chart will be signed to register each therapy performed and will include a log of day and time of device application.

Both electrical stimulation and EMG devices will have disposable pads, after usage they will be discarded. For the Devices they will be placed inside a plastic bag that will be disposed inside the room before exiting and sanitized (wipes) based upon hospital protocols.

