The risk to participants of this study is considered to be minimal in a controlled environment with an attendant present. This research routine will not place subjects at higher risk than normal activities of daily living, and no more risk of harm or discomfort is associated with these tests than the discomfort normally incurred while performing normal muscle stretching. Subjects will be allowed rest time between trials as needed. The EMG device will detect level of fatigue and based on that we will determine the length of the sessions.

The devices and technology is completely non-invasive, safe, non-toxic and non-ionizing. The potential risks to subject are minimal. However, like any battery powered systems, there is a minimum risk of sensor malfunctioning. In addition, the study devices are not waterproof, and although they use a low powered battery (similar to a cellphone battery), in order to avoid any risk of shock the monitor should not be submerged or saturated with fluids during operations or cleaning. It does not emit any radiation to the human body, and does not offer any significant risk to the subject.

Subjects may experience mild discomfort from the sensor on their legs. We will inform the subject to please notify the investigators if the sensor is uncomfortable.

All information we will collect about the subject will be stored in a secure location and coded in a way to maintain confidentiality. Only study personnel will have access to their records. Data collected during the study may be published and made publicly available. Data may also be shared with other research groups. However, data that could in any way identify them will not be made public or shared.

Some of potential risks of using TENS therapy could be: * Skin related discomfort, such as tingling * Skin reaction to adhesive patch.

If the tingling sensation is too intense for the participant, they have the ability to reduce the intensity for their best level of comfort.

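### In Phase I the only stated control on stimulation intensity and the only stated route for reporting discomfort depend on the patient, and no skin check or record is stated for patients who cannot respond

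*Combined protocol and SAP*

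**What the plan says.** **Risks and responses (H1).** The risks listed for stimulation are: "Skin related discomfort, such as tingling * Skin reaction to adhesive patch". On intensity H1 says: "If the tingling sensation is too intense for the participant, they have the ability to reduce the intensity for their best level of comfort". A separate paragraph, on the sensor worn on the legs, says: "We will inform the subject to please notify the investigators if the sensor is uncomfortable". H1 does not distinguish the two phases.

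**Phase I patients.** F1 states: "In some cases, the patients will not able to consent at the time of enrollment". J2 provides for consent by a legal representative and for informing the patient once consciousness returns, and J6 confirms that adults lacking capacity will be enrolled. F1 gives as one aim of the device "muscle activation while the patient is non-responsive to physical activities". It also wants less staff contact, so that "the device will be placed with no additional requirements". Section C adds as background: "All COVID-19 ventilated patients at our institution have been on paralytics for at least 48 hours".

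**Records.** Under F2, Phase I, Aim 2, nurses or other hospital staff give the therapy, and "A chart will be signed to register each therapy performed and will include a log of day and time of device application". Length of stay and major adverse events (MAE, described as including deep vein thrombosis, cardiovascular events and death) come from the health record. Section I lists MAE as a secondary outcome. H2 answers the greater-than-minimal-risk question with no, and no monitoring plan follows.

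**The concern.** The safeguard in H1 suits a patient who is awake and can reach the device or speak to staff. That describes Phase II, where J2 requires patients to be alert and aware, and some of Phase I. It does not describe a Phase I patient who is unconscious at enrolment. For that patient nobody is named to judge whether the intensity is too high, nobody is named to look at the skin under the pads, and no field is described in which either would be written down.

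Section D makes feasibility one of the purposes of Phase I, and how well the therapy is tolerated is part of feasibility. Section I concedes possible skin allergy and unknown risks, and says the devices have not been used for this purpose before. If the plan is followed as written, the information on minor local effects would come mainly from patients able to complain. Silence from the others would carry no information, but a reader could mistake it for absence of harm.

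**Working it through.** The plan gives no figure to reproduce here, so the check sets the passages side by side.

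**Step 1. What each stated control covers.**

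| Control | Where | Needs the patient? | Addresses intensity? | Addresses skin during treatment? |
|---|---|---|---|---|
| Participant lowers intensity | H1 | Yes | Yes | No |
| Subject reports discomfort | H1 (sensor paragraph) | Yes | Not stated | Not stated |
| Session length set from EMG fatigue | H1 | No | No, duration only | No |
| At most 1 hour a day | F2, Aim 2 | No | No, duration only | No |
| Nurse or staff give the therapy | F2, Aim 2 | No | No task stated | No task stated |
| Device check before use | Section I | No | No, malfunction only | No |
| Exclusions, including active wound infection | F1 | No | No | No, entry only |
| Attendant present | H1 | No | No task stated | No task stated |

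Two controls need the patient and six do not. None of the six states a limit on intensity or a skin check.

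**Step 2. Where the named effects would be recorded.** The chart is described as holding day and time of application. MAE are taken from the health record. Neither the outcome list in Section I nor the analysis in G2 mentions skin or stimulation effects.

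**Step 3. Who is affected.** Lack of capacity to consent is not the same as inability to report, since some patients without capacity can still say that something hurts. The firmer evidence is J2, which expects some patients to regain consciousness after enrolment. Their number is not given.

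**Step 4. Exposure.** Inputs: 20 patients and at most 2 weeks (F1); up to 3 sessions a day (F2).

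- Patient-days: 20 × 14 = 280, both arms, nobody discharged early.
- Sessions per patient: 3 × 14 = 42. All patients: 42 × 20 = 840.
- If 25% to 75% of patients cannot report (an assumption), that is 5 to 15 patients and 70 to 210 patient-days.
- Over-intense stimulation concerns only the active arm. With 1:1 allocation (not stated for Phase I), half of that is 35 to 105 patient-days. Patch reaction can occur in either arm.

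The ceiling of 280 rests on F1. F2, Aim 2 has therapy given for the whole hospital stay, with no limit in days.

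**The case against.** The best reply is that the plan has more safeguards than the patient's own report. Trained staff give each session, time is capped, devices are checked, and patients with implanted electronics or infected wounds are excluded. MAE are tracked and analysed, and their list is open-ended. J2 also sends critical information bearing on the patient's well-being to the medical record. These are inpatients, so staff could well notice a skin reaction. All of this stands. A reader might infer that the patient is the only safeguard, or that harm in Phase I is neither limited nor recorded; the documents do not support either reading.

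Three other inferences also go too far. Phase I is not a paralysed population: inability to consent applies to some patients, and the paralytic statement is background on ventilated patients, not an entry criterion. No passage says that these patients cannot feel. The chart is said to include day and time, which does not prove that it has no other field, and the phase-specific consent forms are not available to check.

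It is also fair to say that H1 covers both phases, and that its sentence on intensity describes an ability rather than setting a rule. On that view the text is incomplete rather than contradictory. That lowers the charge but does not answer it: no section says what replaces self-adjustment when the patient cannot adjust, and none of the other safeguards is given that task.

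**Conclusion.** The point holds in a limited form and should be corrected. For Phase I patients who cannot respond, the stated control on intensity and the stated route for reporting discomfort cannot work. Patch reaction has no stated check or response in any patient. With stated harm capture limited to MAE, the skin and stimulation effects that the protocol itself names would not be systematically collected in these patients.

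The exposure is at most 280 patient-days under F1, and the part in patients unable to report is unknown; the 70 to 210 patient-days above are illustrative. The conclusion does not depend on that share, only on its being above zero, which F1 and J2 imply. It does assume that the chart has no further fields than those described.

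A reader might go on to infer that the trial will declare the device well tolerated on this basis. The documents do not support that, because no tolerability endpoint or conclusion is planned for Phase I.

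**What to change.** Reconcile F1, F2 and H1. State in H1 that self-adjustment and self-report apply only to patients able to respond, and state how the same risks are covered for the others. The clinical rule, including any response to a skin reaction, is for the investigators to set.

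On the Phase I therapy chart that staff already sign, add for every session in both arms:

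- skin under the pads at removal (normal or reaction);
- intensity setting;
- session ended early, and why;
- investigator informed (yes or no).

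Tabulate these by arm. Keep the intensity entry away from outcome assessors, since it could reveal the allocation.

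The cost is one edited paragraph, four chart entries and some bedside time. Each assumed minute per session adds at most 280 minutes (about 4.7 hours) over the whole phase with one session a day, and 840 minutes (14 hours) with three. F1 aims to limit staff contact, so the entries should be short and made at pad removal, when staff are already present.

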Physical Activity Monitoring: The subject will be given a wearable device (PAMSys) or a smart watch, that will be measuring several parameters including number of steps taken, duration of sitting, standing, walking and lying, time taken and number of transitions from sit to stand, and walking speed for 48 hours. At the end of the specific visit, the subject will be given the device, if they are given PAMSys it will be attached to pendant to wear around the neck, otherwise they may wear the smart watch on their wrist. Investigators will provide a pre-paid envelope where the subject may place the device and send back it to the investigating team.

Oxygen Level Assessment: Oxygen saturation will be measured using a pulse oximeter.

The supervision of this study will be by pulmonary care specialists, and the location will be at Baylor College of Medicine McNair Campus.

Section G: Sample Size/Data Analysis

G1. Sample Size

How many subjects (or specimens, or charts) will be used in this study? Local: 40 Worldwide: 40

Please indicate why you chose the sample size proposed:

Sample size is convenient and selected based on available resources to demonstrate feasibility and the proof of concept effectiveness of EE therapy for COVID-19 patients admitted to ICU and post-ICU. We plan to recruit 40 eligible subjects.

G2. Data Analysis

Provide a description of your plan for data analysis. State the types of comparisons you plan (e.g. comparison of means, comparison of proportions, regressions, analysis of variance). Which is the PRIMARY comparison/analysis? How will the analyses proposed relate to the primary purposes of your study?

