P-values of 0.05 or less will be considered statistically significant based on a two-sided test unless otherwise noted. All variables will be tabulated descriptively at each scheduled time point (baseline and discharge date). For each continuous variable, the analyses will include the mean, standard deviation, minimum and maximum. For each categorical variable, the summary will include frequencies and percentages. Each variable will be analyzed using all available data. Baseline variables will be summarized using descriptive statistics. We assume that a successful intervention is also helpful to maintain subjects muscle mass, reduce neuromyopathy signs and increase venous return flow. The measured parameters (e.g. muscle circumference, sEMG, kent imaging, doppler, etc.) should change substantially from baseline to the end of the intervention. For example, the EMG amplitude values should show increased voltages. Next, for all continuous variables, pre-treatment scores will be regressed on post-treatment scores to form residualized change scores (e.g. sEMG, VPT, dynamometer, etc). Correlations will then be generated among these scores to determine whether changes in sEMG factors are related appropriately with increases in (clinically assessed) functional capacities and self-report measures of activities. ANOVA test will be used to examine significant difference between patients with severe risk factors for prolonged ICU stage (e.g. age, BMI, cardiovascular morbidities). Moderator effects will also be examined for exploratory purposes. Using gender as an example, mixed design ANOVAs will be conducted to determine whether mobility factors change over the course of treatment at different rates or with different patterns for men and women. Additional analyses will test whether changes in muscle strenght and neuropathy (e.g. VPT and dynamometer assessement at time of discharge).

Section H: Potential Risks/Discomforts

H1. Potential Risks/Discomforts

Describe and assess any potential risks/discomforts; (physical, psychological, social, legal, or other) and assess the likelihood and seriousness of such risks:

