activation. The device is used to reduce pain. However, the proposed treatment may assist in preventing or improving hospital-acquired Weakness because of prolonged hospital stay . In addition, the participation in this study may help the investigators better understand how COVID19 may impact cause myopathy and neuropathy and how to best help these patients to recover from prolonged hospital-stay .

Primary outcomes include neuropathy (assessed using VPT test); muscle function (assessed using sEMG), and tissue oxygenation (assessed using Kent Imaging). Secondary outcomes include weakness (assessed using dynamometer); muscle atrophy (assessed by weight loss as well as measuring ankle, calf, and thigh circumference); venous return flow (Doppler US [optional]); frailty (frailtymeter [optiona]); hospital length of stay (patient medical record); and major adverse events (patient health record). The primary and secondary outcomes will be assessed at baseline (if feasible) and on biweekly basis up to 4 weeks or hospital discharge, whichever came first. Appropriate mixed models (linear for continuous or Generalized Estimating Equations (GEEs) for non-continuous or non-parametric variables) will be used to test the intervention effect for each of the primary (e.g., tissue perfusion, tissue oxygen delivery, neuropathy severity, and myopathy incident) or secondary (e.g., frailty, weight loss, MAE, etc) outcomes.

Also, participation may help the investigators design a practical assessing method to identify the impact of neuromyopathy in the hospital setting. This may allow physicians to provide personalized care by monitoring muscle loss and limb complications caused by prolonged hospital length of stay.

Describe potential benefit(s) to society of the planned work.

As described above, this type of work may allow physicians to provide more personalized care for hospitalized patients in need of physical therapy for continuous and prolonged periods, specially when having a severe illness that includes medical staff risk contact.

Do anticipated benefits outweigh potential risks? Discuss the risk-to-benefit ratio.

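### Tissue perfusion and oxygen delivery are tested as primary outcomes through near-infrared tissue oxygen saturation alone, with no systemic oxygenation recorded at imaging

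*Combined protocol and SAP*

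**What the plan says.** - **Primary vascular measure.** Section I lists "tissue oxygenation (assessed using Kent Imaging". In F1 the corresponding primary outcome, for both phases, is lower-extremity tissue oxygen saturation.
- **What the models test.** The same paragraph of Section I gives the primary outcomes for the mixed models or GEEs as "e.g., tissue perfusion, tissue oxygen delivery, neuropathy severity, and myopathy incident". Neither perfusion nor oxygen delivery has an instrument of its own.
- **Other vascular measures.** Doppler appears among the secondary outcomes as "venous return flow (Doppler US [optional". In the Phase I acute series (F2, Aim 1) it is also optional: "Optional: Subjects will be assessed using Doppler ultrasound and near infrared imaging (Kent Imaging System) at pre-, 30min, 60min, and 30min post-treatment". For Phase II, F2 lists near-infrared spectroscopy as the only vascular assessment, while stating that changes in blood flow will be measured after stimulation.
- **Systemic oxygenation.** Section C says of these patients that "poor blood oxygen saturation, and poor perfusion to lower extremities are other important risk factors". The only planned measure of it is among the optional Phase II assessments in F2: "Oxygen saturation will be measured using a pulse oximeter". J2 adds that optional assessments will not be collected from subjects already enrolled. No section plans to record inspired oxygen or oxygen support at imaging, and no model in G2 or Section I includes systemic oxygenation.
- **Contrast.** F1 defines the primary outcomes as both the between-group difference and the change from baseline. G2, naming Kent imaging among its examples, says the measured parameters "should change substantially from baseline to the end of the intervention".

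**The concern.** Tissue saturation reflects the saturation of the arriving blood as well as local supply and extraction. This is physiological reasoning; the documents do not describe the instrument's output. Section C itself names low blood oxygen saturation and poor leg perfusion as two separate problems, and a single saturation image cannot tell them apart.

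Phase I patients enter within 48 hours of admission for severe infection and are measured again at discharge or 2 weeks. Over that interval lung function and oxygen therapy may change a good deal, and the leg reading can move with them while leg perfusion stays the same. Two things are at stake: whether a rise from baseline is read as a device effect, and whether a saturation result is reported as a finding about perfusion or oxygen delivery.

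**Working it through.** The plan states no power, effect size or SD (G1 calls the sample convenient), so there is no figure to reproduce. Everything below is for scale.

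**Inputs from the documents.** There are 20 patients per phase. Phase II has 10 per arm; Phase I gives no ratio, and 10 per arm is assumed. Tests are two-sided at 0.05 (G2).

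**Assumed inputs.** SD of the local leg change *L* = 4 to 6 points; SD of the arterial saturation change *A* = 2 to 6 points; slope *s* of tissue on arterial saturation from 0.3 to 1; true effect 6 points.

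**1. Shared shift, between arms.** Write each patient's change as shared shift + systemic component + local component. The shared shift cancels in the difference of arm means. In 40,000 simulated trials per setting, with shifts of 0, 0.5 and 1 SD and a systemic share of variance of 0, 10, 30 and 50%, the bias was about 0 and the type I error was 0.048 to 0.052.

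**2. Shared shift, within the intervention arm.** For a one-sample t test with n = 10 (9 df), the noncentrality is shift × √10.
- Shift 0: rejects in 5%.
- Shift 0.5 SD: 0.5 × 3.16 = 1.58; rejects in about 29%.
- Shift 1 SD: 3.16; rejects in about 80%.

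All three figures are with no leg effect.

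**3. Chance imbalance.** The SE of the between-arm difference in mean systemic change is √(2/10) = 0.447 SD.
- P(imbalance > 0.5 SD) = P(|z| > 1.118) = 0.26.
- P(imbalance > 1 SD) = P(|z| > 2.236) = 0.025.
- With *A* = 2 to 6 points, the SE is 0.89 to 2.68 points.

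**4. Power from removing the systemic part.** The raw SD is √(L² + s²A²). With the systemic part removed at a known slope, it is *L*. Two-sample t test, 10 per arm, 6-point effect:

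| L | A | s | Raw SD | Power, raw | Power, systemic part removed |
|---|---|---|---|---|---|
| 6 | 2 | 1 | √40 = 6.32 | 52% | 56% |
| 6 | 4 | 1 | √52 = 7.21 | 42% | 56% |
| 4 | 4 | 1 | √32 = 5.66 | 61% | 89% |
| 4 | 4 | 0.3 | √17.44 = 4.18 | 86% | 89% |

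The last column treats the slope as known. Estimating it as a covariate from 20 patients costs about 2 points: in 40,000 simulated trials the first row gave 54% and the third 87%. In the fourth row the result was 87%, so almost nothing is gained over 86%. A larger *A* at slope 1 would give a larger gain.

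**5. Subtracting arterial saturation instead.** The SD becomes √(L² + (1 − s)²A²). With *L* = *A* = 4:
- s = 0.5: √20 = 4.47, the same as the raw SD, so nothing is gained.
- s = 0.3: √(16 + 7.84) = 4.88, and power falls from 86% to 74%.

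**The case against.** A reader might infer that the primary outcome cannot isolate a leg effect, so that the trial would credit lung recovery to the device. The documents do not support that. F1 randomises both phases against a non-functional device, and the models in Section I test the intervention effect. Step 1 shows no bias in that contrast. If the device itself altered systemic oxygenation, a between-arm difference would still be caused by the device, though not shown to be local.

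G2's remark about substantial change is a loose expectation and not a decision rule, and F1 names the between-group difference first. That is fair. But F1 also makes change from baseline part of the primary outcomes, and nothing in the plan says that within-arm change is only descriptive.

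Scope is a further limit. The argument from poor oxygenation fits Phase I. Phase II patients are alert outpatients treated at home, so it is weaker there. The within-session series (5 minutes or one hour of stimulation in Phase II, up to 30 minutes after stopping in Phase I Aim 1) are too short for lung recovery to matter much, though an oxygen setting changed during a session could.

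A tempting remedy is to make the tissue-minus-arterial difference, or the ratio, the main outcome. Step 5 shows that the difference can lose power, and either form builds the outcome on a value measured after randomisation.

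Finally, higher flow at fixed consumption would raise tissue saturation, so the reading is an indirect index of perfusion. That stands, but an indirect index does not by itself support a conclusion about perfusion or delivery. In a pilot with no power target, the power figures carry little weight.

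**Conclusion.** The point holds in a limited form. Perfusion and oxygen delivery are primary outcomes with no primary instrument except a tissue saturation reading, and the plan does not capture the systemic oxygenation needed to interpret it. Randomisation protects the between-arm test from bias but does not turn a saturation result into a perfusion result.

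Change-from-baseline readings are exposed: false rejection rises from 5% to about 29% or 80% under the assumed shifts. A sizeable chance imbalance between arms, about a one-in-four event at 0.5 SD, would go unseen. Whether adjustment gains power is open: a few points or less in some of the cases worked, up to 28 points with both SDs at 4 and slope 1, and little or none at low slopes. All of these sizes rest on assumed shifts, SDs and slopes. The issue is mainly for Phase I between admission and discharge or 2 weeks.

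**What to change.** 1. Name the outcome tissue oxygen saturation in F1 and Section I, and draw no conclusion about perfusion, oxygen delivery or blood flow from it alone.
2. State that inference rests on the between-arm difference adjusted for baseline tissue saturation, and that within-arm change is descriptive only. Reword F1 and G2 to match.
3. Record pulse-oximeter saturation and inspired oxygen or oxygen support at each image, at least in Phase I. Prespecify a sensitivity analysis with the saturation at imaging as a covariate whose slope is estimated. Do not make a difference or ratio the main outcome.

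**Cost.** One extra reading and two data fields per image, plus the rewording; the pulse oximeter is already Device 7 in Section P. Because the saturation at imaging is measured after randomisation, the sensitivity analysis would remove any device effect that acts through systemic oxygenation. It should therefore stand beside the main analysis and not replace it.
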